7.3. PRECISION

Safety variables (i.e., otoscopy, tympanometry, nasal and epipharynx endoscopy, UPSIT olfactory test, audiology pure tone hearing test, clinical laboratory values, vital signs, and ECG intervals), including derivations thereof, will be reported to the same precision as the source data.

For all PK, and quantitative safety lab data, the precision of the descriptive statistics will be based upon the interpreted number of decimal places or significant figures (according to whichever precision method is applicable for that statistic) of the respective source dataset, defined as the precision of the non-excluded value with the most common precision in the entire source dataset (across all time points and treatment periods, within the subgroup as applicable).

All PK concentrations will be reported and analyzed with the same precision as the source data provided by the bioanalytical laboratory regardless of how many significant figures or decimal places the data carry. Elapsed time variables for PK will be analyzed and reported with 2 decimal places with units of hours. Pharmacokinetic parameters derived by the clinical pharmacokineticist will be considered equivalent to raw data and will be mapped to the CDISC SDTM (Clinical Data Interchange Standards Consortium Study Data Tabulation Model) database using Implementation Guide Version 3.2 without any rounding applied to parameter estimates. All PK parameters will be rounded for reporting purposes in CDISC ADaM (Analysis Dataset Model) datasets and in by-subject listings. The rounded PK parameter

data will be used for the calculation of descriptive statistics and in all statistical analyses. The precision for each PK parameter will be indicated by the clinical pharmacokineticist in the form Pharmacokinetic Review of WinNonlin Analysis (PI_FM_PK0203). Parameters directly derived from source data (e.g., C_{max}) will be analyzed and reported with the same precision as the source data. Actual elapsed sample collection times and parameters derived from them (e.g., t_{max}) will be reported to 2 decimal places with units of hours.

For the reporting of descriptive statistics of Safety, and PK data, the arithmetic mean, GMean (for PK parameters only), SD, median, and confidence intervals (CIs) will be presented to 1 decimal place or significant figure more than the precision of the source data, according to whichever precision method is applicable to the source data provided by the study database, safety laboratory, or bioanalytical laboratory regardless of how many significant figures or decimal places the data carry. The minimum and maximum will be presented to the same decimal place or significant figure precision as the source data, according to whichever precision method is applicable to the source data. All the above statistics for PK concentrations and C_{max} will have precision based on the same precision method interpreted to have been used in the source data. Coefficient of variation, GCV%, and other percentages will always be reported to 1 decimal place.

7.4. REFERENCE START DATE AND STUDY DAY

Study Day will be calculated from the reference start date and will be used to show start/stop day of assessments and events.

Reference start date is defined as the date of the first dose of study medication (Day 1 is the day of the first dose of study medication). Study Day will appear in every listing where an assessment date or event date appears.

- If the date of the event is on or after the reference date, then:
$$\text{Study Day} = (\text{date of event} - \text{reference date}) + 1.$$
- If the date of the event is prior to the reference date, then:
$$\text{Study Day} = (\text{date of event} - \text{reference date}).$$

In the situation where the event date is partial or missing, the date will appear partial or missing in the corresponding SDTM domains and listings. Study Day and any corresponding durations will be imputed in the corresponding ADaM domains as described in APPENDIX 2, Partial Date Conventions. The imputed values will be used for data summarizations as needed.

7.5. BASELINE

Baseline is defined as the last scheduled non-missing measurement taken prior to dosing and will

Document: Statistical Analysis Plan
Author: [REDACTED]

Version Number:
Version Date:

2.0
03APR2019

correspond to: Screening assessment for clinical laboratory; Day -1 assessment for Vital Signs; Day 1 pre-dose assessment for ECG in Cohort A, and the average of the mean triplicate ECG assessments at Day 1, 60 minutes pre-dose and Day 1, 30 minutes pre-dose for ECG in Cohort B; Screening assessment for Physical Examination; Day -1 assessment for Otoscopy, Tympanometry, and Nasal and Epipharynx Endoscopy ; and Screening assessment for University of Pennsylvania Smell Inventory Test (UPSIT) Olfactory test, and Audiology Pure Tone hearing test. However, if a subject is missing the planned baseline collection then the last non-missing evaluation prior to dosing (scheduled or unscheduled), if available, will become the baseline value.

For PK assessments, baseline serum concentration is defined as the mean of the two predose serum concentrations observed in samples collected on Day 1 prior to the first dose. If one predose sample is missing, the other Day 1 predose concentration will be used for baseline correction.

7.6. RETESTS, UNSCHEDULED VISITS AND EARLY TERMINATION DATA

Unscheduled measurements will not be included in summary statistics but will contribute to the best/worst case value where required (e.g. shift tables) and assessment of clinical outliers. Early termination results will be recorded as such and included with the Study Exit visit summaries. In the case of a retest of a scheduled assessment, results from that scheduled time (i.e., the original assessment) will be used for summaries unless flagged as invalid. If results from a scheduled assessment are flagged as invalid, then results from retest assessment will be used for summary.

Listings will include all scheduled, unscheduled, retest, and early discontinuation data.

7.7. COMMON CALCULATIONS

For quantitative measurements, change from baseline will be calculated as:

- Post-baseline Value – Baseline Value

Body Mass Index (BMI) will be calculated as:

- $BMI \text{ (kg/m}^2\text{)} = \text{weight (kg)}/\text{height (m)}^2$

Age will be calculated as:

- $\text{Age (years)} = \text{Integer value of } [(\text{Date of informed consent} - \text{date of birth} + 1)/365.25]$

7.8. SOFTWARE VERSIONS

All derivations, statistical analyses, summaries, plots, and listings will be generated using SAS Version 9.4

Document:	Statistical Analysis Plan	Version Number:	2.0
Author:	[REDACTED]	Version Date:	03APR2019
	[REDACTED]		[REDACTED]
	[REDACTED]		[REDACTED]

or higher (SAS Institute, Inc., Cary, North Carolina). Noncompartmental analysis for PK parameter estimation will be performed using Phoenix® WinNonlin® 6.4 or higher (Certara, L.P., Princeton, New Jersey). Compliance of SDTM and ADaM datasets to CDISC standards will be verified by using the Open CDISC Community tool version 2.0.1 (Pinnacle 21, Plymouth Meeting, Pennsylvania).

8. STATISTICAL CONSIDERATIONS

8.1. SAMPLE SIZE DETERMINATION

The sample size is not based on statistical considerations, but is typical for studies of this nature, and is considered adequate to characterize the distribution of the planned endpoints.

There will be a total of 30 subjects; 2 dose cohorts of 15 subjects each. Subjects will be randomized in 4:1 (OP0201:placebo) ratio to receive either OP0201 or placebo within each dose cohort.

8.2. MISSING DATA

Missing safety data will not be imputed unless otherwise noted in the corresponding sections of this document (e.g., dates, AE severity, AE relationship). Imputed values will be included in the corresponding ADaM but not in the SDTM datasets.

Missing PK concentrations will be handled as described in Section 16.

9. OUTPUT PRESENTATIONS

APPENDIX 1 shows conventions for presentation of data in outputs.

The shells provided with this SAP describe the presentations for this study and therefore are the format and content of the summary tables, listings, and figures to be provided by [REDACTED] Biostatistics.

10. DISPOSITION AND WITHDRAWALS

All entered subjects as defined in the Entered Analysis Set will be accounted for in this study. Subject disposition will be tabulated by cohort and treatment for number of subjects entered, randomized, treated, prematurely withdrew, completed study, and for each reason of premature withdrawal from the study along with the associated percentages. The percentages for the reason of withdrawal for screen failure subjects will be based on the entered set, whereas it will be based on safety set for treated subjects. The tabulation will also be presented for all active treated subjects, all placebo treated

Document: Statistical Analysis Plan
Author: [REDACTED]

Version Number: 2.0
Version Date: 03APR2019

[REDACTED]
[REDACTED]

subjects, and for all subjects combined from both cohorts, irrespective of treatment received, as Overall.

A listing will present dates of completion or early withdrawal and the reason for early discontinuation, if applicable, for each subject. Screen failure subjects will be listed indicating the primary reason of screen failure and will be included in disposition summary tabulations.

Listings of inclusion/exclusion criteria responses, study eligibility during screening and Day -1, and study treatment administration date and times will be provided.

11. DEMOGRAPHIC AND OTHER BASELINE CHARACTERISTICS

Individual subject demographics and baseline characteristics (medical, surgical, and ear history) will be presented in listings.

For the safety analysis set, demographic characteristics such as age, height, weight, and body mass index (BMI) will be summarized by cohort and overall using descriptive statistics. Frequency counts and percentages will be presented for sex, race, and ethnicity. No statistical testing will be carried out for demographic or other baseline characteristics.

12. PROTOCOL DEVIATIONS

12.1. DEVIATIONS RELATED TO STUDY CONDUCT

A protocol deviation is any noncompliance with the clinical trial protocol, GCP, or Manual of Procedure requirements. The noncompliance may be either on the part of the subject, the site PI, or the study site staff. Protocol deviations will be listed including a classification of minor or major, as determined by clinical staff and sponsor.

12.2. DEVIATIONS RELATED TO PK ANALYSIS

Changes to the procedures or events, which may impact the quality of the PK data in Cohort B, will be considered important protocol deviations/events for PK and will be described within the clinical study report body text. These changes or events will include any circumstances that will alter the evaluation of the PK. Examples of important protocol deviation or event include, but are not limited to, administration of prohibited medication, sample processing errors that lead to inaccurate bioanalytical results, inaccurate dosing on the day of PK sampling, and/or non-compliance with dosing to the extent that it is expected to affect the PK objectives of the study. In the case of a significant protocol deviation or event, PK data collected during the affected treatment period will be excluded from the study results. Other changes to the procedures or events which do not impact the quality of the PK data will not be

Document: Statistical Analysis Plan
Author: [REDACTED]

Version Number: 2.0
Version Date: 03APR2019
[REDACTED]

considered significant protocol deviations. A common example of a non-significant protocol deviation is a missed blood sample or deviation from the scheduled time of blood collection at a time unlikely to affect the PK objectives. In contrast, a scheduled pre-dose sample which is erroneously collected postdose would be considered an important deviation leading to exclusion of this data point (and derived PK parameters, if appropriate) from the PK analysis.

Non-compliance with dose administration will be reviewed on a case-by-case basis to determine whether the deviation is expected to affect the PK objectives of the study.

13. MEDICAL, SURGICAL, AND EAR HISTORY

Any relevant medical, surgical, and ear history recorded will be coded using Medical Dictionary for Regulatory Activities (MedDRA) version 21.0. All medical history, including surgical, and ear history will be listed and summarized by System Organ Class and Preferred term for all subjects in the safety analysis set.

14. MEDICATIONS

All medication usage will be coded using the World Health Organization Drug Dictionary (WHO-DD) version 01MAR2018E Format B-2 and listed.

- Prior medications are medications which stopped prior to the first dose of study medication.
- Concomitant medications are medications which were taken during the treatment period, or specifically:
 - started on or after the date and time of first dose of study medication or
 - started prior to the first dose of study medication and were continued after the first dose of study medication

See APPENDIX 2 for handling of partial dates for medications, in the case where it is not possible to define a medication as prior or concomitant, the medication will be classified by the worst case; i.e., concomitant.

15. STUDY MEDICATION EXPOSURE

Study drug administration number within the day (first, second, or third), date and time of administration as well as the total number of sprays administered successfully for each nostril (left and right) will be listed for each administration. Dose administered at each administration will be calculated based on the total number of successful sprays from both nostrils and Overdose Quantity recorded on the CRF using the equation below:

Document: Statistical Analysis Plan
Author: [REDACTED]

Version Number: 2.0
Version Date: 03APR2019

[REDACTED]

Dose administered = (Number of successful sprays in both nostrils x 2.5 mg) + Overdose Quantity

Any protocol deviation or adverse event related to study drug administration will also be included in the listing. Mean daily dose as well as total dose administered over the dosing period of the study will be summarized using descriptive statistics for both cohorts.

Overall compliance will be calculated as:

$$\text{Total Compliance} = 100 \times \frac{\text{actual total number of sprays}}{\text{expected total number of sprays}}$$

where expected total number of sprays is 168 for Cohort A and 336 for Cohort B.

Daily compliance will be calculated as

$$\text{Day}_i \text{ Compliance} = 100 \times \frac{\text{actual number of sprays on Day}_i}{\text{expected number of sprays on Day}_i}$$

where $i = 1$ to 14 and expected number of sprays on Day $_i$ = 12 for Cohort A and 24 for Cohort B.

Compliance for each study day, mean daily compliance, and overall compliance will be listed. Mean daily and overall compliance will be summarized.

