6.4 Study Treatment Compliance

The prescribed dosage, timing, and mode of administration may not be changed, except as defined in Section [6.6](#).

Only subjects enrolled in the study may receive study treatment and only authorized study center staff may administer the study treatment to the subject.

The Investigator or qualified designee will record each dose by noting the time and number of total sprays administered successfully in a dosing log.

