4. STUDY DESIGN

4.1. GENERAL DESCRIPTION

This is a randomized, double-blind, placebo-controlled, parallel-group, dose-escalation study in healthy volunteers to evaluate the safety and tolerability of OP0201 administered intranasally 3 times a day (TID) using a metered dose inhaler (MDI) compared to a matching placebo (HFA-134a minus active ingredients) administered intranasally TID using a MDI for 14 consecutive days (see Figure 1 for the study schematic). The plan is to enroll up to 30 subjects at 1 study center in the US. Two dose cohorts are planned (Cohort A and Cohort B; N=15 per cohort, see Cohort Dosing below, Table 1). Within each cohort, subjects will be randomized in a 4:1 ratio to receive either OP0201 or placebo. After all subjects in Cohort A have completed the Day 14 visit, a Safety Review Committee (SRC) will review all the blinded safety data to determine whether the doses administered are safe and well tolerated. The SRC will make a recommendation to escalate to the next cohort (Cohort B) or not.

Document:	Statistical Analysis Plan	Version Number:	2.0
Author:	[REDACTED]	Version Date:	03APR2019

[REDACTED]

[figure not shown]
[REDACTED]

Table 1 Dose Cohorts and Dose Regimen

Cohort	Dose Regimen	Cohort Dose Allocation		Total Subjects in Each Cohort	Total Subjects Per Dose Group
		Per Day Total Dose (mg)	Cumulative Total Dose (mg)		
A	2 sprays per nostril TID x 14 days	OP0201 (30 mg) ^a Placebo (0 mg)	OP0201 (420 mg) ^a Placebo (0 mg)	15	N=12 (OP0201) N=3 (Placebo)
B	4 sprays per nostril TID x 14 days	OP0201 (60 mg) ^a Placebo (0 mg)	OP0201 (840 mg) ^a Placebo (0 mg)	15	N=12 (OP0201) N=3 (Placebo)

a 2.5 mg per spray

N = number of subjects; TID = three times a day

Figure 1 Study Schema

Document: Statistical Analysis Plan

Author: [REDACTED]

Version Number:

Version Date:

2.0

03APR2019

[figure not shown]

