6.2. SAFETY ANALYSIS SET

The safety analysis set will contain all subjects who are assigned to study treatment and receive at least one dose of any study medication (OP0201 or Placebo) and will be analyzed according to treatment received. Subjects in this population will be used for all safety, dosing, and demographic summaries.

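### The SAP's dose formula applies 2.5 mg per spray to every treated subject, so placebo subjects are credited with 420 or 840 mg where the SAP's own dose table gives 0 mg

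*SAP*

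**What the plan says.** SAP Section 15 calculates the dose at each administration as "Dose administered = (Number of successful sprays in both nostrils x 2.5 mg) + Overdose Quantity". Mean daily dose and "total dose administered over the dosing period of the study will be summarized using descriptive statistics for both cohorts". The same section sets the compliance denominators by cohort alone: "where expected total number of sprays is 168 for Cohort A and 336 for Cohort B".

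SAP Section 6.2 fixes who enters these outputs. The Safety Analysis Set covers assigned subjects who "receive at least one dose of any study medication (OP0201 or Placebo) and will be analyzed according to treatment received", and the section adds: "Subjects in this population will be used for all safety, dosing, and demographic summaries".

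SAP Section 4.1, Table 1, gives the cumulative dose for Cohort A as "OP0201 (420 mg) ^a Placebo (0 mg"), and Cohort B likewise as 840 mg for OP0201 and 0 mg for placebo. The footnote giving 2.5 mg per spray is attached to the OP0201 entries only. Protocol Section 6.1 describes the placebo spray as 0.1 mL of HFA-134a and the OP0201 spray as carrying 2.5 mg of active ingredients in that volume.

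**The concern.** The equation converts sprays to milligrams with a constant that is true for one of the two treatments. Propellant is described by volume, so a milligram figure built on 2.5 mg per spray can only mean active drug. Nothing in Section 15 restricts the equation to OP0201 recipients, and no other part of the SAP sets the placebo dose to zero.

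At stake is whether the exposure table can be believed. A programmer who follows the text would produce an exposure summary in which placebo and active subjects received the same mean amount of drug, contradicting Table 1 of the same document. A second programmer checking the output against the same text would get the same wrong number, so independent programming would not catch it.

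**Working it through.** **Inputs**
- Sprays per nostril per dose: 2 (Cohort A), 4 (Cohort B); two nostrils, three doses a day, 14 days (SAP Table 1).
- Active content of an OP0201 spray: 2.5 mg (SAP Table 1 footnote; Protocol Section 6.1).
- Active content of a placebo spray: 0 mg (SAP Table 1; Protocol Section 6.1).
- Planned allocation in each cohort: 12 OP0201, 3 placebo (SAP Table 1).
- Assumed throughout: full compliance and an Overdose Quantity of zero.

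**Step 1. Reproduce the plan's own figures.** Total sprays = sprays per nostril × 2 × 3 × 14.
- Cohort A: 2 × 2 × 3 × 14 = 168 sprays; 168 × 2.5 = 420 mg.
- Cohort B: 4 × 2 × 3 × 14 = 336 sprays; 336 × 2.5 = 840 mg.

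The spray totals match Section 15 and the doses match the OP0201 entries in Table 1. For OP0201 subjects the formula is correct.

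**Step 2. Apply the same formula to a placebo subject.** The spray count is the same and the formula has no treatment term.
- Each administration: 4 × 2.5 = 10 mg (A) or 8 × 2.5 = 20 mg (B).
- Each day: 12 × 2.5 = 30 mg (A) or 24 × 2.5 = 60 mg (B).
- Whole period: 420 mg (A) or 840 mg (B).

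Table 1 gives 0 mg per day and 0 mg cumulative.

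**Step 3. Carry this into the SAP's display groups.** SAP Section 7.2 pools placebo across cohorts, and SAP Appendix 1 lists the groups. Mean total dose:

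| Group | Formula as written | With placebo at 0 mg |
|---|---|---|
| OP0201 30 mg | 420 mg | 420 mg |
| OP0201 60 mg | 840 mg | 840 mg |
| All Active | (12 × 420 + 12 × 840)/24 = 630 mg | 630 mg |
| All Placebo | (3 × 420 + 3 × 840)/6 = 630 mg | 0 mg |
| All Subjects | (15 × 420 + 15 × 840)/30 = 630 mg | (12 × 420 + 12 × 840)/30 = 504 mg |

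The All Placebo mean daily dose is (3 × 30 + 3 × 60)/6 = 45 mg instead of 0 mg.

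**Step 4. Only if arms are pooled within a cohort.**
- Cohort A: (15 × 420)/15 = 420 mg as written; (12 × 420)/15 = 336 mg with placebo at 0.
- Cohort B: (15 × 840)/15 = 840 mg as written; (12 × 840)/15 = 672 mg with placebo at 0.

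The ratio is 420/336 = 840/672 = 1.25.

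**Step 5. Trace where the milligram value goes.** Compliance in Section 15 is actual over expected sprays, with no milligram term, so it is right for both arms. The SAP names no safety or PK analysis that takes the derived dose as an input.

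**The case against.** The strongest reply is that little depends on this. Table 1 of the same SAP shows placebo as 0 mg, SAP Section 5.3 puts the final analysis after unblinding, and a sensible programmer would set placebo to zero. Section 9 says the table shells define format and content; they are not in the documents and may already do so. It is fair that an attentive team would probably notice. But the derivation is the specification, it states a rule, and that rule gives the wrong value. It should not rely on an output template or on goodwill to be corrected.

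The second reply is that the default display is by treatment group, so the cohort means in Step 4 may never be produced. This stands. The wording "will be summarized using descriptive statistics for both cohorts" can mean simply that Cohorts A and B are both covered. Appendix 1 provides whole-cohort columns for some safety outputs, but nothing says that dose is among them. The reply does not rescue the All Placebo or All Subjects figures, which are wrong under the default display.

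Two stronger readings are tempting and should not be drawn. A reader might infer that the mean active dose is overstated. It is not: the OP0201 30 mg, OP0201 60 mg and All Active values are the same before and after correction. A reader might also infer that sprays given in an overdose are counted twice, because Protocol Section 6.4 has staff record the "number of total sprays administered successfully in a dosing log" and the formula then adds Overdose Quantity. The documents do not show this. Protocol Section 8.4 requires the excess quantity to be documented separately in the eCRF, so two non-overlapping fields that are added is a coherent reading. Without the eCRF pages, overlap cannot be established.

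**Conclusion.** The formula is wrong as written for placebo subjects. With full compliance, no overdose and the planned 12:3 allocation, it credits them with 420 mg (Cohort A) or 840 mg (Cohort B) instead of 0 mg. It makes the All Placebo mean total dose equal to All Active at 630 mg and raises the All Subjects mean from 504 to 630 mg. Actual figures will shift with compliance, but any placebo subject with at least one logged spray gets a non-zero dose. The whole-cohort figures, 420 against 336 mg and 840 against 672 mg, apply only if the arms are pooled within a cohort, which the SAP leaves open.

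The consequence is limited to the exposure listing and summary. A reader might fear that the safety conclusion itself is compromised. The documents do not support that: safety groups are defined by treatment received and labelled by regimen, not by the derived milligrams. This is an inexpensive correction to a reporting rule, not a flaw in the design or the endpoints.

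**What to change.** In SAP Section 15, make the derivation conditional on treatment received: keep the existing expression for subjects who received OP0201, and set dose administered to 0 mg for subjects who received placebo. State that mean daily and total dose are summarised by treatment received. Summarise the number of sprays for all subjects beside the dose, since both arms are exposed to propellant and spray count measures that exposure.

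The cost is a sentence or two of SAP text, one condition in the dataset derivation and one added summary variable. No new data are needed: spray counts are already recorded and listed, and treatment received is known once the study is unblinded.
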